5. ANALYSIS SETS

5.1. Definition

All Enrolled Set

All screened subjects who provide informed consent and provide demographic and/or baseline screening assessments, regardless of the subject's randomization and treatment status in the study and received a Subject ID

All Exposed Set

All subjects in the enrolled set who receive a study vaccination. Safety Set

Solicited Safety Set (solicited local and systemic adverse events and other solicited adverse events)

All subjects in the Exposed Set with any solicited adverse event data and/or indicators of solicited adverse events.

Unsolicited Safety Set (unsolicited adverse events)

All subjects in the Exposed Set with unsolicited adverse event data.

Overall Safety Set

All subjects who are in the Solicited Safety Set and/or Unsolicited Safety Set.

Full Analysis Set Efficacy Not

applicable.

Full Analysis Set Immunogenicity

All subjects in the Enrolled Population who:

- Receive a study vaccination AND provide at least one immunogenicity data at relevant time points.

The FAS will be the primary analysis set for the immunogenicity objective.

In case of vaccination error, subjects in the FAS sets will be analyzed "as randomized" (i.e., according to the study group a subject was assigned).

Per Protocol (PP) Immunogenicity Set All

subjects in the FAS / Immunogenicity who:

- Correctly receive the vaccine.
- Have no protocol deviations leading to exclusion as defined prior to analysis.
- Are not excluded due to other reasons defined prior to analysis.

5.2. Criteria for eliminating data from Analysis Sets

Elimination codes are used to identify subjects to be eliminated from analysis. Detail is provided below for each set. The Full Analysis Set (FAS) will be the primary analysis set for the immunogenicity objective.

A consolidated table is also available in **Annex 2**.

5.2.1. Elimination from Exposed Set (ES)

Code [100/1030](#) (Study vaccine not administered at all) will be used for identifying subjects eliminated from ES

5.2.2. Elimination from Per-protocol analysis Set (PPS)

5.2.2.1. Excluded subjects

A subject will be excluded from the PPS analysis under the following conditions

| Code | Condition under which the code is used |
|-------|--|
| 100 | Study vaccine not administered at all |
| 150 | Administration of concomitant vaccine(s) forbidden in the protocol |
| 120 | Randomization failure |
| 130 | Subjects got vaccinated with the correct vaccine but containing a lower volume |
| 140 | Vaccination not according to protocol |
| 140.1 | Vaccine temperature deviation |
| 140.2 | Expired vaccine administered |
| 200 | Protocol violation (inclusion/exclusion criteria) |
| 230 | Administration of any medication forbidden by the protocol |
| 260 | Subjects did not comply with vaccination schedule |
| 270 | Subjects did not comply with blood sample schedule |
| 110 | Serological results not available post-vaccination |
| 112 | Obvious incoherence or abnormality or error in data |

5.2.2.2. Right censored Data

Data from a subject will be censored from visit x for the PPS analysis under the following conditions. The code ****.X+ will also be used to identify study withdrawal from visit x.

| Code | Condition under which the code is used |
|----------|--|
| 130.x+/- | Subjects got vaccinated with the correct vaccine but containing a lower volume |

5.2.2.3. Visit-specific censored Data

Data from visit x will be censored for the PPS analysis under the following conditions. The code ***.X will also be used to identify study withdrawal from visit X.

| | |
|-------|---|
| Code | Condition under which the code is used |
| 270.x | Subjects did not comply with blood sample schedule at visit x |

5.3. Important protocol deviation not leading to elimination from per-protocol analysis set

Not Applicable.

6. STATISTICAL ANALYSES

Note that standard data derivation rule and stat methods are described in **Annex 1** and will not be repeated below.

6.1. Demography

6.1.1. Analysis of demographics/baseline characteristics planned in the protocol

Descriptive statistics (mean, standard deviation, median, minimum and maximum) for age and BMI at enrolment will be calculated overall.

Distributions of subjects by sex and ethnic origin will be summarized overall.

6.1.2. Additional considerations

Analysis of demography/baseline characteristics will also be shown for the following subgroups:

Shigella group: subjects from parent study H03_01TP who previously received three vaccinations with 1790GAHB.

Placebo group: subjects from parent study H03_01TP who previously received vaccinations with Placebo.

Naïve group: naïve subjects enrolled in H03_01E1TP.

6.2. Exposure

6.2.1. Analysis of exposure planned in the protocol

The frequencies and percentages of subjects with vaccination will be summarized overall. Data will be tabulated for the All Enrolled Set.

6.2.2. Additional considerations

The frequency and percentages of subjects with vaccination will also be summarized for the Shigella, Placebo and naïve group described in **section 6.1.2**.

6.3. Efficacy/Effectiveness

6.3.1. Analysis of efficacy planned in the protocol

Not Applicable. The study has no efficacy objective.

6.4. Immunogenicity

6.4.1. Analysis of immunogenicity planned in the protocol

The FAS will be the primary analysis set for the immunogenicity objective.

Within group assessment

For the immunogenicity profile in terms of anti-LPS *S. sonnei* serum IgG antibody titers, at each timepoint that a blood sample is available, the following parameters (with two-sided 95% Confidence Intervals (CIs)) will be estimated for each treatment group:

- Geometric mean concentration (GMC)
- Seroresponse rate for anti- LPS *S. sonnei* IgG
- Percentage of subjects with post vaccination concentration ≥ 121 EU/ml
- Geometric mean Ratio (GMR): Post vaccination GMC versus baseline (day 1)

In addition, the distribution of antibody titres for Shigella and Placebo+Naïve group for each visit where blood sample was collected will be displayed using reverse cumulative distribution curves.

6.4.2. Additional considerations

The percentage of subjects with seroresponse by titer at baseline and with post vaccination antibody level ≥ 121 IgG units

Pearson CIs will be computed by vaccine group at each visit and associated two-sided 95% Clopper-

Unadjusted GMCs and associated two-sided 95% CIs will be computed for each group at each visit. For each vaccine group, unadjusted GMCs and their 95% CIs will be obtained by exponentiating (base 10) the least square means and the lower and upper limits of the 95% CIs of the log-transformed titers or concentrations (base 10).

Titers below the limit of detection will be set to half that limit for the purposes of analysis. Missing values of immunogenicity will be excluded from analyses (i.e. complete-case analysis) since they are considered missing completely at random, i.e. not informative and with no impact on inferences

The immunogenicity tables will show some or all of the following subgroups. See mock up tables.

Shigella group: subjects from parent study H03_01TP who previously received three vaccinations with 1790GAHB regardless of the total protein amount.

Placebo group: subjects from parent study H03_01TP who previously received vaccinations with Placebo.

Naïve group: naïve subjects enrolled in H03_01E1TP.

Pla+Naïve: subjects from parent study H03_01TP who previously received vaccinations with Placebo plus naïve subjects enrolled in H03_01E1TP

Subjects with detectable antibodies at baseline (i.e. with antibodies at baseline \geq Lower Limit of quantification, LLOQ)

Subjects without detectable antibodies at baseline (i.e. with antibodies at baseline $<$ LLOQ)

Note that in Shigella and Placebo groups the LLOQ was assessed at the baseline of the parent study H03_01TP, while in Naïve group the LLOQ will be assessed at baseline of extended study H03_01TP.

1MG_SHI, 5MG_SHI, 25MG_SHI, 50MG_SHI, 100_MG_SHI: subjects from parent study H03_01TP who previously received vaccinations with GVGH *Shigella sonnei* 1790GAHB vaccine containing 1 mcg, 5 mcg, 25 mcg, 50 mcg, 100 mcg of total protein amount respectively.

6.5. Analysis of safety

6.5.1. Analysis of safety planned in the protocol

All analyses will be based on the ‘as treated’ analysis set. For details please refer to **section 8.4.2.1.2** of the protocol.

All solicited adverse events will be summarized according to defined severity grading scales.

Frequencies and percentages of subjects experiencing each adverse event will be presented for each symptom severity. Summary tables showing the occurrence of any local or systemic adverse event overall and at each time point will also be presented.

6.5.2. Additional considerations

The safety tables will be shown for following subgroups. See also H03_01E1TP mock up tables.

Shigella group: subjects from parent study H03_01TP who previously received three vaccinations with GVGH *Shigella sonnei* 1790GAHB regardless of the total protein amount.

Pla+Naïve: subjects from parent study H03_01TP who previously received vaccinations with Placebo plus naïve subjects enrolled in H03_01E1TP

Total: All subjects enrolled in H03_01E1TP study (Shigella Group plus Pla+Naïve group)

6.5.2.1. Exclusion of implausible solicited Adverse Event

Some local and systemic adverse events will be directly measured by the subject and will not be subject to a reconciliation process, even if they are biologically implausible. Therefore these implausible measurements will be removed from the analysis but included in listings. Implausible measurements are summarized in the table below:

Table 6.5.2.1-1 Implausible Solicited Adverse Events

| Parameter | Implausible measurements |
|------------------|---|
| Body temperature | $\leq 33^{\circ}\text{C}$ or $\geq 42^{\circ}\text{C}$ |
| Erythema | For subjects ≥ 6 years: ≥ 900 mm Measurements < 0 mm |
| Induration | For subjects ≥ 6 years: ≥ 500 mm Measurements < 0 mm |

6.5.2.2. Solicited Adverse Events

Post-vaccination solicited adverse events reported from 30 min after vaccination to day 7 will be summarized by maximal severity and by vaccine group.

The severity of solicited local adverse events, including injection-site erythema and induration will be summarized according to categories based on linear measurement: 25 to 50 mm, 51 to 100 mm, >100 mm.

Injection site pain/tenderness and systemic adverse events (except fever) occurring up to 7 days after vaccination will be summarized according to “mild”, “moderate” or “severe”.

Each solicited local and systemic adverse event will also be further summarized as “none” versus “any”. For injection-site erythema and induration any is defined as ≥ 25 mm.

Implausible measurements (for further definition see statistical analysis plan) will be left out of the analysis.

Use of antipyretics and analgesics will be summarized by frequency and percentage of subjects reporting use.

Body temperature will be summarized by 0.5°C and 1.0°C increments from 36.0°C up to $\geq 40^{\circ}\text{C}$.

Body temperature will be broken down by route of measurement according to the recommendations of the Brighton collaboration and will be summarized according to the 3 schemes described below:

- by 0.5 °C increments:
<36.0,
36.0 -
36.4,
36.5 -
36.9,
37.0 -
37.4,
37.5 -
37.9,
38.0 -
38.4, 38.5 - 38.9, 39.0 - 39.4, 39.5 - 39.9, $\geq 40.0^{\circ}\text{C}$
by 1.0 °C increments: <36.0, ≥ 36.0 -<37.0, ≥ 37.0 -<38.0, ≥ 38.0 -<39.0, ≥ 39.0
 $\geq 40^{\circ}\text{C}$
-<40,
- <38.0 ,
 ≥ 38.0
°C
Fever,
defined
as a
body
temperat
ure of
 $\geq 38^{\circ}\text{C}$
irrespect
ive of
route of
measure
ment,
will be
integrate
d to the
summar

es as a
systemic
adverse
event.

The analyses will encompass summaries of the data on four levels:

1. Daily reports of subjects with solicited adverse events.
2. Time of first onset of solicited adverse events.
3. Solicited adverse events, maximum event severity by event and interval From 30 Min through Day 7.
4. Solicited adverse events and indicators of solicited adverse events, occurrence of at least one event by category (local, systemic) and interval From 30 Min through Day 7.

For each of the time points or time intervals presented in the summaries, only subjects with at least one plausible observation (i.e., any non-missing values but excluding “Not done/unknown” and implausible values) for the solicited adverse events will be considered. Subjects without plausible data (i.e. missing values or reported as “Not done/unknown” and implausible values) will be removed from the denominator to prevent a downward bias (towards zero). Level 1: Daily reports of solicited adverse event

For each of the time points only subjects with at least one plausible observation (i.e., any non-missing values but excluding “Not done/unknown” and implausible values) for the solicited adverse event in the interval of interest will be considered. Subjects without plausible data (i.e. missing values or reported as “Not done/unknown” and implausible values) will be removed from the denominator in order to prevent a downward bias (towards zero). Data collected will be summarized (frequencies and percentages of subjects) by vaccine group, solicited adverse event and time point.

Level 2: Time of first onset of solicited adverse events

The time of first onset is defined, for each subject, for each solicited adverse event, as the time point at which the respective solicited adverse event first occurred. For erythema, induration the following threshold(s) will be used ≥ 25 mm. The summary will provide the frequencies and percentages of subjects with first onset of each solicited adverse events by vaccine group and by each time point.

Level 3: Solicited adverse events, maximum event severity by event and interval

The **maximum event severity** will be defined if there is at least one plausible nonmissing observation (excluding “Not done/unknown” and implausible values) within this time interval, Each subject’s data will be aggregated across the time points of the interval and summarized according to the maximal severity observed for each adverse event, followed by a summary across subjects for each vaccine. Subjects without any solicited adverse

events in the interval, i.e., missing values at each of the requested time points, will be removed from the denominator.

Level 4: Solicited adverse events, occurrence of at least one event by category (local, systemic) and interval.

The **occurrence of at least one solicited adverse event** is defined as “any” (≥ 25 mm for erythema and induration) for a subject if he/she reports greater than “none” for the respective event and “none” otherwise. The occurrence of at least one solicited adverse event (i.e., none versus any) will be summarized by category (i.e., local, systemic, any) by vaccine group.

Medications to treat or prevent pain or fever will be summarized by frequencies and percentages of subjects reporting use of the medications from 30 min to day 7.

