8.4.2.1.2 Analysis of Solicited Local, Systemic and Other Adverse Events

All solicited adverse events will be summarized according to defined severity grading scales.

Frequencies and percentages of subjects experiencing each adverse event will be presented for each symptom severity. Summary tables showing the occurrence of any local or systemic adverse event overall and at each time point will also be presented.

Post-vaccination solicited adverse events reported from day 1 to day 7 will be summarized for the intervals day 1-3, day 4-7, day 1-7 by maximal severity and by vaccine group, excluding the 30 minute and 4 hour measurement, which will be summarized separately. The severity of solicited local adverse events, including injectionsite erythema and induration will be summarized according to categories based on linear measurement: 25 to 50 mm, 51 to 100 mm, >100mm.

Injection site pain/tenderness and systemic adverse events (except fever) occurring up to 7 days after vaccination will be summarized according to “mild”, “moderate” or “severe”.

Each solicited local and systemic adverse event will also be further summarized as “none” versus “any”.

Implausible measurements (for further definition see statistical analysis plan) will be left out of the analysis.

Use of antipyretics and analgesics will be summarized by frequency, by type of use (prophylactic versus treatment) and percentage of subjects reporting use. The influence of antipyretics and analgesics use on the occurrence of specific adverse events (e.g., fever, pain) will be assessed.

Body temperature will be summarized by 0.5 °C and 1.0 °C increments from 36.0 °C up to ≥ 40 °C.

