9. CHANGES FROM PLANNED ANALYSES

Not Applicable.

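### SAP Level 3 reports maximal severity of solicited events over one 30-minute-to-Day-7 window, whereas the protocol sets three intervals with the 30-minute and 4-hour readings kept apart, and SAP section 9 declares no change

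*SAP*

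**What the plan says.** **Protocol.** Under section 8.4.2.1.2, the solicited reactions of the first week "will be summarized for the intervals day 1-3, day 4-7, day 1-7 by maximal severity and by vaccine group". The same sentence then keeps the two clinic readings out of these intervals and gives them a summary of their own: "excluding the 30 minute and 4 hour measurement, which will be summarized separately". The clinic readings are made at about 30 minutes and 4 hours, while the subject is under observation (Table 2, note e; section 5.2.1). The subject's own diary starts at about 6 hours (section 3.4.2).

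**SAP.** Section 6.5.2.2 replaces this with one window: "Post-vaccination solicited adverse events reported from 30 min after vaccination to day 7 will be summarized by maximal severity and by vaccine group". Level 3 is defined as "Solicited adverse events, maximum event severity by event and interval From 30 Min through Day 7", with the rule "Each subject’s data will be aggregated across the time points of the interval and summarized according to the maximal severity observed for each adverse event". Level 4 covers "occurrence of at least one event by category (local, systemic) and interval From 30 Min through Day 7". Level 1 is by time point: "Data collected will be summarized (frequencies and percentages of subjects) by vaccine group, solicited adverse event and time point". Level 2 gives first onset by time point. Annex 2 (Table 12-1) defines one solicited safety set, for the period from 30 minutes to Day 7. Day 1-3 and Day 4-7 do not appear in the SAP. Section 9, "CHANGES FROM PLANNED ANALYSES", is marked as not applicable, although the document history shows that the SAP was written against the current protocol, version 2.

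**The concern.** The trial is descriptive, with no hypotheses and no success criteria, so the tables are themselves the result for secondary safety endpoint b (solicited reactions in the 7 days after vaccination). The protocol keeps two kinds of observation apart: readings taken in the clinic in the first hours, and what the subject records at home afterwards. Level 3 takes one maximum across both. It also removes the split between the first three days and the last four.

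The report would then give severity distributions that are not the ones prespecified. Because section 9 declares no change, nothing would tell the reader so.

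**Working it through.** The documents give no solicited-event rate, so there is no stated figure to reproduce. The check has three parts.

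**1. The two rules side by side (maximal-severity summary)**

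| Item | Protocol 8.4.2.1.2 | SAP 6.5.2.2, Level 3 |
|---|---|---|
| Intervals | Day 1-3, Day 4-7, Day 1-7 | 30 minutes through Day 7 only |
| 30-minute and 4-hour readings | Excluded, summarized separately | Inside the window, not excluded |
| Declared as a change | n/a | No (section 9) |

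**2. Can the protocol's figures be rebuilt from the SAP's tables?**

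- *Maximal severity by interval: no.* It needs each subject's grades linked across days. Take two hypothetical subjects, both severe on Day 1, and grant that Level 1 is split by grade. In case A, one is moderate on Day 4 and mild on Day 5, and the other is mild then moderate. In case B, one is moderate on both days and the other is mild on both. Level 1 (one moderate and one mild on each day), Level 2 (both first onset Day 1) and pooled Level 3 (both severe) are identical. The Day 4-7 maxima are two moderate in case A, but one moderate and one mild in case B.
- *Day 1-7 rate without the clinic readings: only bounded.* Let P be the number of subjects with the event in the pooled window, and F the number whose first onset was at 30 minutes or 4 hours (Level 2). Level 2 does not show whether those F subjects also had the event later. Denominators aside, the count without the clinic readings lies between P − F and P. The width is F/n, which is 1/20 = 5.0 percentage points per such subject in the Shigella group.

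**3. How far could the rates differ?**

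Planned maximum group sizes (protocol Table 1; SAP Table 2-1):

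- Shigella: 5 + 4 + 2 + 4 + 5 = 20
- Pla+Naïve: 4 + 26 = 30
- Total: 50

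Each subject whose only event is at a clinic reading adds 1/20 = 5.0 points, 1/30 = 3.3 points or 1/50 = 2.0 points respectively. A subject whose worst grade is at a clinic reading, but who also has a milder diary event, moves up a severity category without changing the any-event rate.

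Illustration, with both inputs assumed: let p be the Day 1-7 rate without the clinic readings, and q the share of the remaining subjects with an event only at a clinic reading. The pooled rate is p + q(1 − p), so the shift is q(1 − p). For q from 0 to 20%:

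- p = 20%: 0 to 0.20 × 0.80 = 16 points
- p = 50%: 0 to 0.20 × 0.50 = 10 points
- p = 80%: 0 to 0.20 × 0.20 = 4 points

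The denominator can work the other way. The SAP keeps any subject with at least one plausible observation in the interval. A subject with clinic readings but no diary data, and no event, counts in the pooled table and not in a diary-only one. As an example, 10/19 = 52.6% becomes 10/20 = 50.0%.

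**The case against.** Several points on the other side are sound, and they limit what can be claimed.

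- **Early events stay visible.** A reader might infer that early reactogenicity can no longer be told from later reactogenicity. The SAP does not support that. Level 1 gives occurrence and Level 2 gives first onset, both by time point. First onsets are mutually exclusive, so summing them through Day 3 gives cumulative incidence to that day, with clinic readings included and missing data aside.
- **Level 4 does not breach the protocol.** A reader might extend the point to the any-versus-none tables. The protocol attaches its intervals to the maximal-severity summary only. It names no interval for none versus any, and it asks for occurrence overall and at each time point.
- **The pooled window is not wrong for the endpoint.** A reader might conclude that the pooled rate is inflated. Endpoint b covers the 7 days after vaccination, which does not exclude the first hours. The shift may be zero, upward or downward. The conflict is with the reporting rule in protocol 8.4.2.1.2.
- **SAP 6.5.1 refers to protocol 8.4.2.1.2 for details**, and 6.5.2 is headed as additional considerations, so the protocol intervals might be taken as retained. This does not settle the matter. The specific rule in 6.5.2.2, its four listed levels and the single analysis set in Annex 2 all use the one window. At best the SAP contradicts itself.
- **The 4-hour reading is not named in the SAP's solicited-event text.** Its pooling is inferred from a window that contains it and does not exclude it. Annex 3 relies on standard mock tables that are not in the documents, so the final layout cannot be checked.

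**Conclusion.** The inconsistency stands for Level 3. The SAP's single window replaces the three intervals and the separate clinic-reading summary that protocol version 2 prespecifies, without declaring it. Two things are lost from the planned tables: maximal severity by interval, and the Day 1-7 rate without the clinic readings, which Level 2 only bounds.

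The effect on the reported rates cannot be determined. The per-subject steps of 5.0 and 3.3 points assume full planned enrolment of 20 and 30; smaller groups give larger steps. The 0 to 16 point range rests on assumed rates and indicates scale only. The conclusion itself rests on the wording of the two documents, and on reading the specific rules of SAP 6.5.2.2 as prevailing over the general cross-reference in 6.5.1.

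**What to change.** In SAP 6.5.2.2, Level 3, tabulate maximal severity for Day 1-3, Day 4-7 and Day 1-7, excluding the 30-minute and 4-hour readings. Summarize those two readings in their own table or columns, as protocol 8.4.2.1.2 requires. State the denominator for each interval, since a subject may have clinic readings but no diary data.

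The pooled window from 30 minutes to Day 7 may be kept as an additional summary, including for Level 4, provided that section 9 lists it as a change and gives the reason.

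The cost is SAP wording and some programming on data already collected. The downside is a longer table.
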